Week 3 (Days 15-21)	100 P (am) + 100 P (am) 200 (pm) + 200 (pm)	100 P (am) + 100 (am) 200 P (pm) + 200 (pm)	100 (am) + 100 (am) 200 (pm) + 200 (pm)	100 P (am) + 100 P (am) 200 P (pm) + 200 P (pm)
Week 4 (Days 22-28)	200 P (am) + 200 P (am) 200 (pm) + 200 (pm)	200 P (am) + 200 (am) 200 P (pm) + 200 (pm)	200 (am) + 200 (am) 200 (pm) + 200 (pm)	200 P (am) + 200 P (am) 200 P (pm) + 200 P (pm)
Week 5 (Days 29-35)	200 P (am) + 200 P (am) 200 (pm) + 200 (pm) + 200 P (pm)	200 P (am) + 200 (am) 200 (pm) + 200 (pm) + 200 P (pm)	200 (am) + 200 (am) 200 (pm) + 200 (pm) + 200 (pm)	200 P (am) + 200 P (am) 200 P (pm) + 200 P (pm) + 200 P (pm)

Table 6-2 Titration Regimen

Visit	Weeks (Days)	Tablet regimen for all groups
Baseline*	Week 1 (Days 1-7)	Take 2 tabs in the morning and 2 tabs in the evening from the blister
	Week 2 (Days 8-14)	Take 2 tabs in the morning and 2 tabs in the evening from the blister
	Week 3 (Days 15-21)	Take 2 tabs in the morning and 2 tabs in the evening from the blister
	Week 4 (Days 22-28)	Take 2 tabs in the morning and 2 tabs in the evening from the blister
	Week 5 (Days 29-35)	Take 2 tabs in the morning and 3 tabs in the evening from the blister
Week 4# (Day 28)	Week 6 (Days 36-42) to Week 8 (Days 50-56)	Take 1 tab from AM Bottle 1 and 2 tabs from AM Bottle 2; repeat the process in the night with PM bottles.

* = Subjects will be given 5 blister wallets (for Weeks 1-5)

= Subjects will be given 2 sets of 2 Bottles as mentioned.

Table 6-3 Treatment Schedule: Treatment Period (Weeks 6-24)

Visit	PPC-06 400 mg QD Regimen	PPC-06 400 mg BID Regimen	PPC-06 600 BID Regimen	PPC-06 Placebo BID Regimen
	Week 6 – Week 24	Week 6 – Week 24	Week 6 – Week 24	Week 6 – Week 24
Weeks 8-20 (Dispense 2 sets of 2 Bottles) ¹	200 P (am) + 200 P (am) + 200 P (am) 200 (pm) + 200 (pm) + 200 P (pm)	200 P (am) + 200 (am) + 200 (am) 200 (pm) + 200 (pm) + 200 P (pm)	200 (am) + 200 (am) + 200 (am) 200 (pm) + 200 (pm) + 200 (pm)	200 P (am) + 200 P (am) + 200 P (am) 200 P (pm) + 200 P (pm) + 200 P (pm)

¹ Subjects will be given 2 sets of 2 bottles (2 morning (AM) bottles + 2 evening (PM) bottles)

AM Bottles: AM Bottle 1 (30 count) and AM Bottle 2 (60 count)

PM Bottles: PM Bottle 1 (30 count) and PM Bottle 2 (60 count)

Take 1 tablet from (AM) Bottle 1 and 2 tablets from (AM) Bottle 2; repeat the process in the evening with (PM) bottles

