8.5 Study Medication/Visit Compliance

The number of doses received by each subject and the number of days exposed to study medication will be summarized by treatment group and study period (titration, treatment, overall) using summary statistics (mean, standard deviation [SD], median, minimum, and maximum), and categorically.

The percent of subjects compliant with study medication at each visit will be presented by study period and overall.

Following are the compliance parameters:

- Total number of tablets taken during the titration period (Week 1-5), defined as number of dispensed tablets from blister wallets minus number of returned tablets from blister wallets.
- Total number of tablets taken during the treatment period (Week 6 – 24), defined as total number of dispensed tablets from bottles minus total number of returned tablets from bottles.
- Number of tablets taken per bottle during the treatment period (Weeks 6 - 24), defined as number of dispensed tablets per bottle (total of 4 bottles per visit) minus number of returned tablets per bottle (total of 4 bottles per visit).
- Total number of tablets taken, defined as the summation of number of tablets taken during the titration and the treatment period.
- Percent compliance will be calculated as the number of tablets taken divided by the expected number of tablets, as defined for the titration period, treatment period and overall.
- Subject compliance, defined as 80% - 120% (inclusive) in percent. If the percentage of study medication compliance is unknown, the subject is assumed to be non-compliant with study medication.
- The average daily dose of IP received can be calculated as the number of tablets divided by the number of days exposed to study medication.

- The average daily dose of IP received by each subject will be summarized by visit, treatment group using summary statistics (mean, SD, median, minimum, and maximum), for the overall period.

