## 12.4 Study Medication Exposure and Compliance

The following exposure and compliance parameters will be summarized by treatment group and study period (overall, titration, and treatment as applicable) using descriptive statistics:

- Total number of days exposed to study medication, defined as date of last dose of study drug during the study minus date of first dose of study drug plus 1.
- Total number of tablets taken during the titration period (Week 1 – 5), defined as number of dispensed tablets from blister wallets minus number of returned tablets from blister wallets.
- Total number of tablets taken during the treatment period (Week 6 – 24), defined as total number of dispensed tablets from bottles minus total number of returned tablets from bottles.
- Number of tablets per bottle taken during the treatment period (Week 6 – 24), defined as number of dispensed tablets per bottle (total of 4 bottles per visit) minus number of returned tablets per bottle.
- Total number of tablets taken, defined as the summation of number of tablets taken during the titration and treatment period.
- Percent compliance will be calculated as the number of tablets taken divided by the expected number of tablets, defined for the titration period, treatment period, and overall. The expected number of tablets are as following:

Period	Number of Tablets Dispensed Per Dosing Regimen	Expected Total Number of Tablets
Titration (Week 1 – 5)	Week 1 – 4: 28 per week Week 5: 35 per week	$28*4 + 35 = 147$
Treatment (Week 6 – 24)	42 per week	$42*19 = 798$
Overall (Week 1 – 24)		945

- Subject compliance, defined as 80% - 120% (inclusive) in percent compliance. If the percentage of study medication compliance is unknown, the subject is assumed to be non-compliant with study medication. Subject compliance is summarized by periods and overall. Overall compliance will be the main determinant of compliance.
- Average daily dose of IP received can be calculated as the number of tablets divided by the number of days exposed to study medication. The average daily dose of IP received by each subject will be summarized by treatment group using summary statistics for the overall period.

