Yes	XX (XX.X)	XX (XX.X)	XX (XX.X)	XX (XX.X)
No	XX (XX.X)	XX (XX.X)	XX (XX.X)	XX (XX.X)

[1] Date of last dose of study drug during the study minus date of first dose of study drug plus 1

[2] Summation of number of tablets taken during the titration and treatment period

[3] Number of tablets taken divided by the number of days exposed to study medication.

[4] Number of tablets taken / number of expected tablets \*100. The expected total number of tablets is 945 for the whole study.

Table 14.1.3.2: Summary of Exposure and Compliance  
Titration Period (Week 1—5)  
Safety Population

	PPC-06 400 mg QD (N=XX)	PPC-06 400 mg BID (N=XX)	PPC-06 600 mg BID (N=XX)	Placebo (N=XX)
Total Number of Tablets Taken [1]				
N	XX	XX	XX	XX
Mean (SD)	XX.X (XX.X)	XX.X (XX.X)	XX.X (XX.X)	XX.X (XX.X)
Median	XX.X	XX.X	XX.X	XX.X
Minimum, Maximum	XX, XX	XX, XX	XX, XX	XX, XX
Percent Compliance (%) [2]				
N	XX	XX	XX	XX
Mean (SD)	XX.X (XX.X)	XX.X (XX.X)	XX.X (XX.X)	XX.X (XX.X)
Median	XX.X	XX.X	XX.X	XX.X
Minimum, Maximum	XX, XX	XX, XX	XX, XX	XX, XX
80-120% Compliant (Inclusive), n (%)				
N	XX	XX	XX	XX
Yes	XX (XX.X)	XX (XX.X)	XX (XX.X)	XX (XX.X)
No	XX (XX.X)	XX (XX.X)	XX (XX.X)	XX (XX.X)

[1] Number of dispensed tablets from blister wallets minus number of returned tablets from blister wallets.

[3] Number of used tablets / number of expected tablets for the titration period \*100. The expected total number of tablets is 147 for the titration period.

Generated on XX/XX/XX:XXXX by XXXXXX / Uses: XXXX / Reference: Listing XXXX

Table 14.1.3.3: Summary of Exposure and Compliance  
Treatment Period (Week 6 – 24)  
Safety Population

	PPC-06 400 mg QD (N=XX)	PPC-06 400 mg BID (N=XX)	PPC-06 600 mg BID (N=XX)	Placebo (N=XX)
Total Number of Tablets Taken [1]				
N	XX	XX	XX	XX
Mean (SD)	XX.X (XX.X)	XX.X (XX.X)	XX.X (XX.X)	XX.X (XX.X)
Median	XX.X	XX.X	XX.X	XX.X
Minimum, Maximum	XX, XX	XX, XX	XX, XX	XX, XX
Percent Compliance (%) [2]				
N	XX	XX	XX	XX
Mean (SD)	XX.X (XX.X)	XX.X (XX.X)	XX.X (XX.X)	XX.X (XX.X)
Median	XX.X	XX.X	XX.X	XX.X
Minimum, Maximum	XX, XX	XX, XX	XX, XX	XX, XX
80-120% Compliant (Inclusive), n (%)				
N	XX	XX	XX	XX
Yes	XX (XX.X)	XX (XX.X)	XX (XX.X)	XX (XX.X)
No	XX (XX.X)	XX (XX.X)	XX (XX.X)	XX (XX.X)

[1] Number of dispensed tablets from bottles minus number of returned tablets from bottles.

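### The 'average daily dose of IP' row counts tablets, active and placebo alike, so it does not measure the PPC-06 dose received

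*SAP*

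**What the plan says.** SAP 12.4 gives the rule: "Average daily dose of IP received can be calculated as the number of tablets divided by the number of days exposed to study medication". Protocol 8.5 words it almost identically. Footnote [3] of the Table 14.1.3.1 shell in SAP section 16 repeats it ("Number of tablets taken divided by the number of days exposed to study medication"), as does footnote [3] of Listing 16.2.5.3. The table row carries no unit and has a placebo column.

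The numerator is all study tablets. SAP 12.4 states: "Total number of tablets taken, defined as the summation of number of tablets taken during the titration and treatment period". Each part is dispensed minus returned, from blisters and from bottles, with no split into active and placebo and no weighting by strength. The expected count is not given by arm; the table footnote says: "The expected total number of tablets is 945 for the whole study". Protocol Table 6-2 explains why, under the column heading "Tablet regimen for all groups": everyone takes the same number of tablets, and Tables 6-1 and 6-3 show placebo tablets filling the gap in the lower-dose arms. Protocol 6.1 gives two active strengths, 100 mg and 200 mg.

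The SAP defines no exposure measure in mg.

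**The concern.** The trial compares three doses with placebo. A reader would expect a row titled average daily dose to separate the arms, and to show how far the dose received fell short of the dose assigned after missed doses, reductions and early stopping. A count of tablets per day does not do this. Assigned dose does not enter the formula, and a non-zero 'dose' would be reported for placebo. The row can also rank subjects in the wrong order, because the schedule rises from 4 to 6 tablets a day: anyone who stops early scores lower, whatever mg they took. At stake is how dose-response and safety by arm are read from the exposure table.

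**Working it through.** **Inputs.** Tablets per week come from SAP 12.4: 28 in Weeks 1–4, 35 in Week 5 and 42 in Weeks 6–24. Active mg per day is the sum of the tablets not marked P in Protocol Table 6-1 (Weeks 1–5) and Table 6-3 (Weeks 6–24). The full course is 24 × 7 = 168 days: 35 of titration and 133 of treatment.

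**The plan's own count.** 28 × 4 + 35 = 147; 42 × 19 = 798; 147 + 798 = 945. This reproduces.

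**The rule at full adherence.** 945/168 = 5.625 tablets per day in every arm (147/35 = 4.2 in titration, 798/133 = 6.0 in treatment).

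**Scheduled active dose**, as [7 × (sum of mg/day over Weeks 1–5) + 133 × (mg/day in Weeks 6–24)] / 168:

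| Arm | mg/day, Weeks 1 to 5 | mg/day, Weeks 6–24 | Total mg | Mean mg/day | SAP row |
|---|---|---|---|---|---|
| 400 mg QD | 100, 200, 400, 400, 400 | 400 | 7 × 1,500 + 133 × 400 = 63,700 | 379 | 5.625 |
| 400 mg BID | 100, 200, 300, 400, 600 | 800 | 7 × 1,600 + 133 × 800 = 117,600 | 700 | 5.625 |
| 600 mg BID | 200, 400, 600, 800, 1,000 | 1,200 | 7 × 3,000 + 133 × 1,200 = 180,600 | 1,075 | 5.625 |
| Placebo | 0 | 0 | 0 | 0 | 5.625 |

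**Early stopping with full adherence until then, any arm.**
- Day 28: 112/28 = 4.0.
- Day 56: (147 + 21 × 6)/56 = 273/56 = 4.875.
- Day 84: (147 + 49 × 6)/84 = 441/84 = 5.25.

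So a 600 mg BID subject who stops at Day 56 scores 4.875, having averaged (21,000 + 21 × 1,200)/56 = 825 mg/day. A 400 mg QD completer scores 5.625 on 379 mg/day. The order is reversed. Early stopping matters here because SAP section 7 assumes 50% dropout.

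**Temporary reduction.** Protocol 6.3 removes one tablet from each Bottle 2, so 6 tablets become 4: a fall of 33% in every arm. The fall in mg depends on what Bottle 2 holds, which the documents do not state. If it holds the two like tablets of each trio in Table 6-3 (an assumption), the fall is 400 to 200 mg (50%) in 400 mg QD, 800 to 400 mg (50%) in 400 mg BID and 1,200 to 800 mg (33%) in 600 mg BID.

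**The case against.** The best defence is that the quantity is openly defined wherever it appears, its arithmetic is sound, and IP is also used for blinded study medication in general. Protocol 6.6.2 speaks of placebo IP, and the safety population and FAS require a dose of IP, which must include placebo subjects. On that usage, tablets of IP per day is a legitimate figure for all four arms. This part stands: as a tablet count nothing is miscalculated. But the Protocol Introduction identifies IP with PPC-06, and even on the wider usage a count of tablets of differing content is not a dose. The strength mix is the lesser issue, since 100 mg tablets appear only in Weeks 1 and 3; the active/placebo mix runs through the whole course.

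A reader might infer three stronger things that the documents do not support:

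- That the four arms will report the same value. The equality is the scheduled one, at full adherence to Day 168. Observed means will differ.
- That the row is blind to interruptions and reductions. Both lower tablets per day, though not in proportion to mg, and Listings 16.2.5.1 and 16.2.5.2 show returns by weekly blister and by bottle.
- That efficacy or safety inference is compromised. The co-primary models in SAP 12.8.1 compare randomized arms, the adverse-event rates in 12.9.1 use subject-days, and percent compliance is properly a tablet ratio.

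**Conclusion.** The point holds as one of definition and labelling. Under the stated rule the row cannot distinguish arms whose scheduled averages run from 0 to 1,075 mg/day. Any difference it shows between arms will reflect adherence, reductions and time of stopping, not assigned dose. The mg figures rest on full adherence for 168 days and on Tables 6-1 and 6-3 as printed; the mg effect of a reduction rests in addition on the assumed bottle contents. The consequence is limited to descriptive exposure reporting. It is a minor point, worth correcting because a dose-ranging report should state the dose received.

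**What to change.** Rename the row in SAP 12.4, Table 14.1.3.1 and Listing 16.2.5.3 as average number of tablets per day, with that unit. Add a row for average daily mg of PPC-06: active mg taken divided by days exposed, zero for placebo.

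Two items must be settled in the text:

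- **Kit contents.** Tables 6-1 and 6-3 do not say which tablet is in which bottle, so the program needs the kit-content list as well as the per-bottle counts.
- **Blister returns.** Listing 16.2.5.1 gives only the number returned per weekly wallet, and most active-arm wallets mix tablet types. In Week 3 of 400 mg BID, one returned tablet could be 0, 100 or 200 mg. State an allocation rule, for example pro rata to the scheduled mg for that arm and week (here 300/4 = 75 mg per tablet).

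The cost is SAP wording, a lookup table and programming after unblinding, with no new data collection. The downside is that titration-period mg is approximate. At full adherence that period supplies 10,500/63,700 = 16%, 11,200/117,600 = 10% and 21,000/180,600 = 12% of total mg in the 400 mg QD, 400 mg BID and 600 mg BID arms; the share is larger for early stoppers.

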## 12.5 Prior and Concomitant Medications

Prior (within the previous 30 days and with stop dates prior to first dose of study drug) and concomitant (ongoing or with stop dates on or after first dose of study drug) medications will be presented for the safety population in a by-subject listing for each treatment group. If the medication is ongoing or the stop year is missing, the medication will be considered as received for the entire duration of the study. Medications will be coded using WHO-DD terminology.

For the determination of prior vs concomitant medications, the following rules regarding the stop date will be applied:

- If only year was recorded, and it is before Baseline, it is a prior medication; if year is same or after Baseline, it is assumed to be a concomitant medication.
- If day is missing, but month and year are before Baseline, it is a prior medication; if month and year are the same as Baseline, it is assumed to be a concomitant medication; if month and year are after Baseline, it is a concomitant medication.
- If start date is after Baseline, it is a concomitant medication regardless.

In addition, prior and concomitant medications will be summarized by treatment, WHO-DD Anatomical-Therapeutic-Chemical (ATC) classification and preferred term (PT).

## **12.6 Medical History and Concurrent Procedures**

Medical history (including previous and ongoing medical conditions) will be coded using MedDRA and presented in a by-subject listing.

Psoriasis Medical History, Prior Psoriasis Treatment History and Other Medical/Surgical History will be presented in separate by-subject listings.

Concurrent procedures will be coded using MedDRA and presented in a by-subject listing.

## **12.7 Efficacy Endpoints**

### **12.7.1 Primary Efficacy Endpoint**

The co-primary efficacy endpoints are as follows:

- The proportion of subjects who achieve a reduction of 75% or greater from Baseline in the Psoriasis Area and Severity Index (PASI-75) at the end of Week 24
- The proportion of subjects who achieve an IGA score of clear or almost clear (IGA score 0 or 1) at the end of Week 24

### **12.7.2 Secondary Efficacy Endpoints**

The secondary endpoints are the following:

- Change from Baseline and percent change from Baseline in total PASI Score by Visit in the Double-Blind Treatment Period
- Proportion of subjects who achieve PASI-50 and PASI-75 at each visit in the Double-Blind Treatment Period
- Proportion of subjects who achieve an IGA score of clear or almost clear at each visit in the Double-Blind Treatment Period
- Change from Baseline and percent change from Baseline in percent of affected BSA at each visit in the Double-Blind Treatment Period
- For applicable subjects present with non-zero baseline NAPSI score (score range 0-8) in target nail, change from baseline in Nail Psoriasis Severity Index (NAPSI) of the target fingernail at Weeks 12, 16 and 24
  - All fingernails will be scored at Baseline and the target nail will be selected as the one with the worst (highest) score by investigator; Only the target nail will be evaluated in the subsequent visits.
  - If a target nail was not identified on the CRF, for purpose of analysis, it will be selected programmatically as the fingernail with the worst score at Baseline. If more than 1 nail has the same worst score, then the target nail will be the first nail according to the order of digit collected on the CRF (i.e., digit 1/thumb, digit 2...digit 5). If the same digit from both hands have the same worst score, the target nail will be selected from the left hand.
  - If score is 0 at Baseline, then the respective assessments at future visits would not be required.
- For applicable subjects present with non-zero baseline score, change from baseline by visit in Psoriasis Scalp Score Index (PSSI, score range 0-72) and Palmoplantar Psoriasis Physician's Global Assessment (PP PGA, score range 0-4) in the Double-Blind Treatment Period;
  - If score is 0 for PSSI and PP PGA at Baseline, then the respective assessments at future visits would not be required;
- Change from Baseline and percent change from Baseline in pruritus Numeric rating scale (NRS) score (score range 0-10) at each visit in the Double-Blind Treatment Period
- Time to achieving a PASI-75 response, defined as time in days from baseline to first achieving a reduction of 75% or greater from Baseline in PASI. Subjects who did not achieve PASI-75 by the last assessment or withdrew prior to the last study visit will be censored at their last PASI assessment

- Time to achieving an IGA score of clear or almost clear, defined as time in days from baseline to first achieving an IGA score of 0 or 1. Subjects who did not achieve an IGA of 0 or 1 at the last assessment or withdrew prior to the last study visit will be censored at their last IGA assessment

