### **12.8.2 Secondary Efficacy Analyses**

All secondary efficacy analyses will be performed on the FAS and PP populations.

The following categorical secondary efficacy endpoints will be summarized using the number and percentage of subjects within each category for each treatment group. A same logistic regression model as used for the primary endpoint will be performed. Each PPC-06 group will be compared to placebo separately as described in the primary analysis.

- Proportion of subjects who achieve PASI-50 and PASI-75 by visit in the Double-Blind Treatment Period
- Proportion of subjects who achieve an IGA score of clear or almost clear by visit in the Double-Blind Treatment Period

The observed values and change from baseline in PP PGA will be summarized as categorical endpoint using frequency counts and percentages. The change from baseline in severity categories will be compared between treatment groups using a Wilcoxon rank sum test.

The following continuous secondary efficacy endpoints will be summarized descriptively and analyzed using an Analysis of Covariance (ANCOVA) including factors for treatment, baseline

BMI, and pooled analysis center. Each PPC-06 group will be compared to placebo separately. The least square mean (LSM) difference, along with the 95% CI and p-value will be reported.

- Change from Baseline and percent change from Baseline in total PASI Score by visit in the Double-Blind Treatment Period
- Change from Baseline and percent change from Baseline in percent of affected BSA by Visit in the Double-Blind Treatment Period
- For applicable subjects, change from baseline in NAPSI of the target fingernail at Weeks 12, 16 and 24
- For applicable subjects, change from baseline by visit in PSSI in the Double-Blind Treatment Period
- Change from Baseline and percent change from Baseline in pruritus NRS score by Visit in the Double-Blind Treatment Period

The following time to event variables will be analyzed using the Kaplan-Meier (KM) method. Subjects who have not achieved treatment response by the last visit or discontinue the study will be censored at their last visit. The mean, 25th, 50th, and 75th percentile time to achieving a treatment success will be reported; log-rank test will be performed for the comparison between each PPC-06 arm and placebo.

- Time to achieving PASI-75 response
- Time to achieving IGA 0 or 1

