Median	XX	XX	XX	XX
75th percentile	XX	XX	XX	XX
Log Rank Test p-Values				
PPC-06 vs. Placebo	0.XXX	0.XXX	0.XXX	
PPC-06 vs. PPC-06 600 mg BID	0.XXX	0.XXX		
PPC-06 vs. PPC-06 400 mg BID	0.XXX			

Note: PASI= Psoriasis Area and Severity Index

[1] Days from baseline to first achieving a reduction of 75% or greater from Baseline in PASI. Subjects who did not achieve PASI-75 by the last assessment or withdrew prior to the last study visit will be censored at their last PASI assessment.

Generated on XX/XX/XX:XXXX by XXXXX / Uses: XXXX / Reference: Listings XXXX

Table 14.2.2.11: Analysis of Secondary Efficacy Outcome  
 Time to Achieving an IGA Score of Clear or Almost Clear  
 Full Analysis Set, OC

	PPC-06 400 mg QD (N=XX)	PPC-06 400 mg BID (N=XX)	PPC-06 600 mg BID (N=XX)	Placebo (N=XX)
Time to Achieving an IGA Score of Clear or Almost Clear [1]				
Kaplan-Meier Estimates				
N	XX	XX	XX	XX
25th percentile	XX	XX	XX	XX
Median	XX	XX	XX	XX
75th percentile	XX	XX	XX	XX
Log Rank Test p-Values				
PPC-06 vs. Placebo	0.XXX	0.XXX	0.XXX	
PPC-06 vs. PPC-06 600 mg BID	0.XXX	0.XXX		
PPC-06 vs. PPC-06 400 mg BID	0.XXX			

Note: IGA= Investigator's Global Assessment

[1] Days from baseline to first achieving an IGA score of 0 or 1. Subjects who did not achieve an IGA of 0 or 1 at the last assessment or withdrew prior to the last study visit will be censored at their last IGA assessment.

Generated on XX/XX/XX:XXXX by XXXXX / Uses: XXXX / Reference: Listings XXXX

Table 14.2.3.1: Analysis of Quality of Life Outcome  
Change from Baseline in QIDS-SR16 Total Score by Visit  
Full Analysis Set, OC

	PPC-06 400 mg QD (N=XX)	PPC-06 400 mg BID (N=XX)	PPC-06 600 mg BID (N=XX)	Placebo (N=XX)
Baseline				
N	XX	XX	XX	XX
Mean (SD)	XX.X (XX.X)	XX.X (XX.X)	XX.X (XX.X)	XX.X (XX.X)
Median	XX	XX	XX	XX
Minimum, Maximum	XX, XX	XX, XX	XX, XX	XX, XX
Week 12				
N	XX	XX	XX	XX
Mean (SD)	XX.X (XX.X)	XX.X (XX.X)	XX.X (XX.X)	XX.X (XX.X)
Median	XX	XX	XX	XX
Minimum, Maximum	XX, XX	XX, XX	XX, XX	XX, XX
Change from baseline				
N	XX	XX	XX	XX
Mean (SD)	XX.X (XX.X)	XX.X (XX.X)	XX.X (XX.X)	XX.X (XX.X)
Median	XX	XX	XX	XX
Minimum, Maximum	XX, XX	XX, XX	XX, XX	XX, XX
<Repeat for Week 16, Week 24>				

Note: QIDS-SR16=Quick Inventory of Depressive Symptomatology-Self Report (16 Items). OC = Observed Cases.

Generated on XX/XX/XX:XXXX by XXXXXX / Uses: XXXX / Reference: Listings XXXX

Table 14.2.3.2.1: Analysis of Quality of Life Outcome  

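### The censoring rule for time to PASI-75 and time to IGA 0/1, as worded, censors subjects who had already responded, contrary to the SAP's own first-response definition

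*SAP*

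**What the plan says.** SAP 12.7.2 gives the event for PASI-75 as "defined as time in days from baseline to first achieving a reduction of 75% or greater from Baseline in PASI" and for IGA as "defined as time in days from baseline to first achieving an IGA score of 0 or 1". Protocol 4.2.1 defines both endpoints in the same way and gives no censoring rule. Neither document requires the response to last.

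The censoring rule appears in three places in the SAP:

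- **12.7.2, PASI-75:** "Subjects who did not achieve PASI-75 by the last assessment or withdrew prior to the last study visit will be censored", at the last PASI assessment.
- **12.7.2, IGA:** dated to the last IGA assessment, the rule covers any subject described by "did not achieve an IGA of 0 or 1 at the last assessment or withdrew prior to the last study visit will be censored".
- **12.8.2, both endpoints:** "Subjects who have not achieved treatment response by the last visit or discontinue the study will be censored at their last visit".

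The footnotes of the table shells in Section 16 repeat the 12.7.2 wording: "Subjects who did not achieve PASI-75 by the last assessment or withdrew prior to the last study visit" in Table 14.2.2.10 and "Subjects who did not achieve an IGA of 0 or 1 at the last assessment or withdrew prior to the last study visit" in Table 14.2.2.11. The analysis is Kaplan-Meier with a log-rank test of each dose against placebo, on the FAS with observed cases (SAP Section 9 and 12.8.2).

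**The concern.** If the event is the first response, it is complete at the first qualifying visit, and nothing later can undo it. The censoring sentences do undo it, in two ways.

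First, not responding and withdrawing are joined by *or*, and the second condition is not confined to non-responders. A subject who reaches PASI-75 at Week 8 and withdraws at Week 16 meets it and is censored after the event was observed.

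Second, the IGA rule turns on status *at* the last assessment, while the PASI rule asks whether response was achieved *by* it. A subject with IGA 1 at Week 12 and IGA 2 at the end is censored under 12.7.2 but has an event under the first condition of 12.8.2. The censoring date also differs: last PASI or IGA assessment in 12.7.2, last visit in 12.8.2.

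At stake are the Kaplan-Meier percentiles and log-rank p-values of two secondary endpoints, in a trial planned with 50% dropout. Two programmers could draw different curves from the same data and each point to the text.

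**Working it through.** **1. The wording, case by case**

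| Subject | First-response definition | 12.7.2 and footnotes | 12.8.2 |
|---|---|---|---|
| PASI-75 at Week 8, withdraws at Week 16 | event, Week 8 | censored | censored |
| IGA 1 at Week 12, IGA 2 at last assessment, completes | event, Week 12 | censored | event |
| IGA 1 at Week 12, still 0/1 when withdrawing at Week 16 | event, Week 12 | censored | censored |
| Never responds | censored, date not defined | censored, last assessment | censored, last visit |

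The first three rows contradict the definition in at least one place. The second row also sets two SAP sections against each other.

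**2. The plan's own figure**

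The documents give no figure for these endpoints. The only one built on the same response and dropout inputs is the co-primary power of at least 84% (SAP Section 7): 15% against 45%, 50 completers per arm, two-sided 0.05.

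- z = [0.30 − 1.96 × √(2 × 0.30 × 0.70/50)] / √(0.15 × 0.85/50 + 0.45 × 0.55/50) = (0.300 − 0.180)/0.0866 = 1.39, so power is 0.918 per endpoint.
- Two endpoints, taken as independent: 0.918² = 0.842. This agrees with the SAP.

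The censoring rule does not enter this figure.

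**3. Size of the withdrawal clause (illustration)**

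Assumptions not in the documents: six visits; constant per-visit chance of first response, reaching c by Week 24 (0.45 active, 0.15 placebo, borrowing the SAP's Week 24 rates); constant per-visit chance of withdrawal with nominal total d; withdrawal independent of response.

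- Per-visit response chance: h = 1 − (1 − c)^(1/6).
- Events under the first-response rule: E = h × (1 − a⁶)/(1 − a), with a = [(1 − c)(1 − d)]^(1/6).
- Events under the literal rule: L = c × (1 − d)^(5/6). Only subjects still present at Week 24 can have an event.

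| Arm, d | h | a | E | Still in at Week 24 | L | Lost, 1 − L/E |
|---|---|---|---|---|---|---|
| Active, 0.50 | 0.0948 | 0.8064 | 0.355 | 0.561 | 0.253 | 29% |
| Placebo, 0.50 | 0.0267 | 0.8671 | 0.116 | 0.561 | 0.084 | 27% |
| Active, 0.25 | 0.0948 | 0.8628 | 0.406 | 0.787 | 0.354 | 13% |
| Placebo, 0.25 | 0.0267 | 0.9277 | 0.134 | 0.787 | 0.118 | 12% |

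A simulation of 100,000 subjects per scenario agrees for the three rows it covered (it did not run placebo at 0.25). At nominal 50% dropout, active events fall from 35.5 to 25.2 per 100 and the Kaplan-Meier response by Day 168 from 0.45 to 0.35; the placebo estimate falls from 0.15 to about 0.115. The gap between arms narrows from 0.30 to about 0.235.

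**4. Adding the IGA last-assessment condition**

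With an assumed 10% or 20% chance per visit of losing response, the same simulation at nominal 50% dropout leaves 19.8 or 15.9 active IGA events per 100, a total loss of about 44% or 55%. This applies only if 12.7.2 is followed rather than 12.8.2.

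**The case against.** The strongest reply is that this is loose drafting. Censoring ordinarily applies to subjects without the event, so the withdrawal condition was probably meant for those who left before responding. The *at* in the IGA sentence looks like a slip, because the parallel PASI sentence and 12.8.2 both say *by*. These are two secondary endpoints outside the sequential co-primary procedure, and the literal rule lengthens response times and weakens the tests, which is the conservative direction for an efficacy claim.

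Much of this stands. The intended rule may well be the sensible one, and the consequence is limited. But no sentence in either document confines the withdrawal condition to non-responders, 12.8.2 repeats it, and the footnotes that a programmer would follow carry the literal text. Where protocol and SAP differ, Protocol 8.10 lets the SAP prevail.

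A reader might also infer that the loss falls mainly on the active arms, because subjects who leave for poor tolerability would be on active drug, and that the comparison is therefore biased. The documents do not support this. They plan the same 50% dropout in every arm, and under independent withdrawal the proportional losses are nearly equal (29% and 27%). More events are lost on active in absolute number only because more occur there. Nor do the documents say how many dropouts will have responded first, so no single loss can be claimed for this trial.

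**Conclusion.** The point holds as a conflict between a stated censoring rule and the endpoint definition it serves. It has three parts: the withdrawal clause (both endpoints, all places); the last-assessment condition for IGA (12.7.2 and the Table 14.2.2.11 footnote, against 12.8.2); and the inconsistent censoring date. If programmed as written, it lowers the estimated response curves and weakens the log-rank tests.

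The percentages are illustrations: they rest on constant per-visit rates, independent withdrawal and, for IGA, assumed rates of losing response. Differential loss between arms remains a possibility, not a finding. The co-primary analyses and their stated power are untouched. It should be corrected because it is a pre-specification error with an easy remedy, not because it threatens the main conclusion.

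**What to change.** Use one rule in SAP 12.7.2, SAP 12.8.2 and the footnotes of Tables 14.2.2.10 and 14.2.2.11:

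> Subjects with a response at any assessment in the on-treatment analysis windows (Visits 3-8, Section 11.4) have an event at the date of the first such response, regardless of later withdrawal or loss of response. Only subjects with no such response are censored, at their last on-treatment PASI or IGA assessment.

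The limit to on-treatment windows matters. PASI and IGA are also collected at the early termination and Week 25 visits (Protocol Table 1-1), and SAP 11.4 treats assessments more than 15 days after the last dose as off-treatment. A rule covering any post-baseline visit would admit those.

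State also how a first response after the start of rescue medication is handled, in line with the treatment-failure convention already in SAP Sections 8 and 9.

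The cost is SAP and shell wording only. No data collection, sample size or co-primary analysis changes.
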